### 7.2 Recruitment Plan

Several recruitment strategies will be employed, and sites within each network will use a combination of methods depending on their capabilities. Specific recruitment strategies are as follows (non-comprehensive list):

1. Networks and sites with electronic health record abilities will query electronic health records based on study enrollment criteria and create screening lists for individual site PIs, which will be forwarded to site research personnel in the early summer months prior to each enrolling season.
2. Subjects will be enrolled prior to discharge from a hospitalization for acute heart failure or myocardial infarction if found no longer to be acutely decompensated.
3. Enrollment will occur as part of an outpatient visit in a cardiology or primary care clinic, cardiac rehab visit, or other clinical setting prior to routine influenza vaccination campaigns. The enrolling sites will generally be cardiology specialty clinics with a large volume of myocardial infarction or heart failure patients. Potential participants will be approached by a member of the health care team to assess interest in participating in INVESTED.
4. When feasible, letters will be mailed to potential subjects (identified either through electronic queries or through clinic patient lists), reminding them to get vaccinated during the fall months and informing them about the INVESTED study.
5. Potential subjects may undergo an initial eligibility screen by phone.
6. Individual sites may use additional strategies for which IRB approval will be obtained prior to implementation.

It is anticipated that a large portion of subjects will be identified prior to the start of influenza season, while the remainder will be enrolled from mid-August through January. Influenza vaccine is typically available at the end of August, and it is crucial to recruit individuals early prior to their routine receipt of influenza vaccine. Initial study visits will be scheduled in advance to commence when annual formulations of each study vaccine will be available for use in the trial.

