## 9.3 Correlative Studies Procedures

**9.3.1 Immune Response Sub-study**, for a subset of subjects only, after the Vanguard year. This sub-study is optional for sites. Subjects participating in the immune response sub-study (up to 1,000 per year) will be scheduled for a follow-up visit between two-four weeks (+ 4 days) post-vaccination. Subjects unable to participate for a follow up blood draw will not be included in the immune response sub-study. Subjects may participate in the immune response sub-study multiple years.

Blood will be drawn to assess antibody titers. Among a subset of sub-study subjects who agree to it, additional blood will be collected for future research about other biomarkers, and genetics.

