## **12.0 CORRELATIVE (IMMUNE RESPONSE, BIOMARKER AND DNA) STUDIES**

Antibody titers to influenza vaccine antigens, seroprotection, and seroconversion will be assessed in a subgroup of subjects (up to 3,000 subjects, approximately 1,000 subjects from each of the three influenza seasons) to test the hypothesis that a higher influenza vaccine dose will result in more pronounced humoral immune response, evidenced by greater mean titers post-vaccination and higher antibody titer changes from baseline, and to test the hypothesis that higher antibody concentrations will be associated with the reduced rate of the composite of all-cause death and cardiopulmonary hospitalization. Participation in correlative studies is optional.

Additional blood will be collected from a further subset of correlative study subjects for future research about biomarkers and DNA.

A subset of approximately 35 sites from geographically diverse regions in the US and Canada will be asked to participate in the humoral immune response sub-study.

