3. STUDY DESIGN

The INVESTED trial is a randomized, double-blind, active-controlled, multi-site trial comparing high-dose (60 µg per vaccine viral strain) trivalent influenza vaccine (HD-TIV) to standard-dose (15 µg per viral strain) quadrivalent influenza vaccine (SD-QIV) for up to three influenza seasons in 9,300 high-risk cardiovascular disease patients with a history of acute myocardial infarction (MI) in the previous 12 months or a history of heart failure (HF) hospitalization in the previous 24 months. Subjects will be randomized in a 1:1 ratio to HD-TIV or SD-QIV, using permuted blocks of random block size, balanced by site, without stratification, except for the natural stratification by influenza season. The total trial duration is four years including site initiation, a Vanguard season followed by three influenza seasons, and follow-up until the end of the last influenza season.

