8.6 Analysis of the Correlative Endpoints for the Immune Response Substudy

Antibody titers at baseline and week 4, change in antibody titers from baseline to week 4, and the incidence of seroconversion and seroprotection in A/H1N1, A/H3N2 and B-type vaccine antigens and in A/H1N1, A/H3NW and B-Yamagata lineage at 4 weeks following vaccinations will be summarized with descriptive statistics such as geometric mean and standard deviation or median and IQR for quantitative measures and frequency and proportion for qualitative measures along with graphics such as box plots or empirical distribution functions and bar plots and compared between the two treatment arms using two-sample tests with robust variance to account for intra-subject correlation over multiple vaccinations.

Clinical outcomes will be compared between those with and those without overall seroconversion and seroprotection and antigen-specific seroconversion and seroprotection to A/H1N1, A/H3N2, B-Yamagata and B-Victoria vaccine antigens (for standard dose vaccine) and to A/H1N1, A/H3N2 and B-Victoria lineage (for high dose) using log-rank

tests. Cox proportional hazards regression analysis will be performed for the primary endpoint of the composite of all-cause death or cardiopulmonary hospitalization with the geometric mean titer across vaccine strains post-vaccination as a model term, instead of individual antibody titers, to avoid issues of collinearity, stratified by enrolling season, while adjusting for other covariates including treatment and other immune responses and the interaction between treatment and match for circulating B-Yamagata lineage that is included only in the standard-dose QIV (binary), based on influenza typing and subtyping data. The hazard ratio for each doubling of the geometric mean titer will be estimated along with confidence intervals from Cox proportional hazards regression analysis with robust variance estimation. Given that the traditional definition of seroprotection, namely HAI titers ≥ 40 , may be an inadequate estimate of a protective threshold during years of poor match between vaccine antigens and circulating strains, we will also assess seroprotection defined as HAI ≥ 80 , 160, and 320 as exploratory analyses.

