8.9 Analysis of Safety Endpoints

The analysis of the safety endpoints will follow the mITT analysis used for the primary efficacy endpoints. The primary safety endpoint is incidence of vaccine injection site reactions such as injection site reactions (e.g. erythema, pain, or redness), and systemic side effects including headache, myalgia, and fever. The number and percentage of subjects experiencing vaccine injection site reactions will be summarized by treatment arm and by enrolling season, and the incidence will be compared using nonparametric methods such as chi-square tests. Incidence of vaccine injection site over multiple seasons will be considered independent.

The secondary safety endpoint is incidence of vaccine-related adverse events and serious adverse events and will be analyzed as above for the primary safety endpoint.

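### The between-arm immune comparisons in SAP 8.6 pool seasons without a season term, which makes the tests somewhat conservative; adding enrolling season is a free, minor improvement

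*SAP*

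**What the plan says.** SAP 8.6 covers baseline and week-4 titers, titer change, seroconversion and seroprotection. These are to be "compared between the two treatment arms using two-sample tests with robust variance to account for intra-subject correlation over multiple vaccinations". That correction is needed only when one subject supplies observations from more than one season, which Protocol 9.3.1 allows: "Subjects may participate in the immune response sub-study multiple years". No season stratum, season term or by-season analysis is named. Protocol 13.7 adds nothing on season for this comparison.

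Season bears on the measurement itself. Protocol 7.2 refers to the time when "annual formulations of each study vaccine will be available for use in the trial", and Protocol 12.0 defines the outcome on the vaccine strains: "Antibody titers to influenza vaccine antigens, seroprotection, and seroconversion will be assessed in a subgroup of subjects". Recruitment is "approximately 1,000 subjects from each of the three influenza seasons". Protocol 12.1.1 has each cryovial labelled with its collection season and allows batch shipment at the end of each season.

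Elsewhere the plan does account for season:
- SAP 3 describes randomization as "without stratification, except for the natural stratification by influenza season".
- The primary log-rank test and Cox model (SAP 8.3.1) are stratified by enrolling season.
- The titer-outcome Cox model in SAP 8.6 uses the geometric mean titer "to avoid issues of collinearity, stratified by enrolling season".
- Injection site reactions in SAP 8.9 are "summarized by treatment arm and by enrolling season".
- Protocol 13.18.2 calls for findings to be post-stratified by age group, cardiovascular risk group and influenza season, with season defined as the cohort year enrolled.

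**The concern.** The antigens behind the labels A/H1N1, A/H3N2 and B can differ from one season to the next, and so can the assay batch. Mean titers may then move between seasons for reasons unrelated to dose. A two-sample test on pooled observations counts that movement as random error. Robust variance clustered on subject handles repeat participation but does not remove a difference between seasons.

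At stake is precision for the dose-response hypothesis in SAP 2.3.1: standard errors that are too wide, a true type I error below the nominal 5%, and some lost power for small differences. This is a correlative endpoint in an optional sub-study; the primary efficacy analysis is not affected.

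**Working it through.** **No figure to reproduce.** The documents state no power, effect size or SD for the immune sub-study.

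**Inputs from the documents.** Up to 3,000 observations, about 1,000 in each of three seasons (Protocol 12.0); 1:1 allocation (SAP 3); two-sided 0.05 (SAP 8.11).

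**Assumed inputs.** Within-season SD of log2 titer (w) 1.5 to 2.0; SD of season means (t) 0.25 to 1.0; 80% power for the stratified test as the reference point.

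**Formulas.** With equal numbers per arm within each season, season means cancel in the arm difference, so the pooled point estimate is no noisier than the stratified one. Only its estimated standard error is inflated, by r = sqrt(1 + (t/w)²). Hence:
- true type I error = 2 × [1 − Φ(1.96 r)]
- power = Φ(2.80 − 1.96 r), where 2.80 = 1.96 + 0.84

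| t | w | r | Type I error | Power (80% if stratified) |
|---|---|---|---|---|
| 0.25 | 1.5 | 1.014 | 0.047 | 0.79 |
| 0.25 | 2.0 | 1.008 | 0.048 | 0.80 |
| 0.5 | 1.5 | 1.054 | 0.039 | 0.77 |
| 0.5 | 2.0 | 1.031 | 0.043 | 0.78 |
| 0.75 | 1.5 | 1.118 | 0.028 | 0.73 |
| 0.75 | 2.0 | 1.068 | 0.036 | 0.76 |
| 1.0 | 1.5 | 1.202 | 0.018 | 0.67 |
| 1.0 | 2.0 | 1.118 | 0.028 | 0.73 |

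**In units of the step between seasons.** Let adjacent seasons differ by s within-season SDs. For three equal seasons r = sqrt(1 + 2s²/3): 1.02 at s = 0.25, 1.08 at 0.5 and 1.29 at 1.0. For two seasons r = sqrt(1 + s²/4): 1.03 at s = 0.5 and 1.12 at 1.0.

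**Check with repeat subjects.** A simulation used 3,000 observations over three seasons, 35% of each later season returning, intra-subject correlation 0.5 and subject-clustered variance (1,000 runs per setting; all values assumed). For an effect of 0.115 SD, power without and with season terms was 0.78 and 0.79 at s = 0.25, 0.76 and 0.80 at s = 0.5, and 0.67 and 0.81 at s = 1.0. Clustered variance alone did not recover the loss.

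**Larger effects.** With independent observations, 80% power at N = 3,000 corresponds to 2.80 × sqrt(2/1500) = 0.10 SD. For an effect of 0.2 SD, 0.2/sqrt(2/1500) = 5.48, so even at r = 1.202 power is Φ(5.48 − 2.36), above 0.99. At N = 2,000 it is Φ(4.47 − 2.36) = 0.98.

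**Seroprotection.** The ratio is sqrt[p̄(1 − p̄) / mean of p(1 − p)]. Assumed season rates of 0.7/0.8/0.9 give sqrt(0.1600/0.1533) = 1.02; rates of 0.5/0.75/0.95 give sqrt(0.1956/0.1617) = 1.10.

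**The case against.** The strongest reply is that Protocol 13.18.2 already requires post-stratification by influenza season, and that SAP 1.2, which lists only the dropped congenital heart disease analysis, does not withdraw it. SAP 8.6 never calls its tests unstratified. This softens the point but does not settle it. SAP 8.6 does not carry the provision into these tests, and cohort year enrolled is the sampling season only for first-year subjects. A returning subject's serum is assayed in a later season.

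The second reply is that the size rests on assumptions and that plausible dose effects are large. This largely stands. No document lists strains or shows titers shifting. Protocol 5.3 cites a 414-subject comparison of the two dose levels with p < 0.01 for both A strains and p = 0.04 for B. Taking equal arms of 207 and a simple two-sample test, these imply at least 2.58 × sqrt(2/207) = 0.25 SD and about 2.05 × sqrt(2/207) = 0.20 SD. Those were older adults rather than cardiac patients, but effects of that size keep high power either way.

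Third, titer change and seroconversion compare two samples against the same season's antigens, so part of the shift cancels. That stands too.

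Fourth, SAP 6 gives a data cutoff of July 31, 2019. As the sub-study starts after the Vanguard year, two seasons may remain rather than three. That lowers r for a given step between adjacent seasons and also reduces the sample; the omission remains.

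**Conclusion.** The point holds as a minor matter of precision. SAP 8.6 omits season from its between-arm immune comparisons, out of line with its own Cox model. For post-vaccination titer the estimated standard error is about 1% to 20% too large over the assumed range. At a season SD of 1.0, type I error is about 2-3% and power about 67-73% instead of 80%. The loss is small for steps of up to about half a within-season SD between seasons, smaller for titer change, seroconversion and seroprotection, and of little consequence for effects of 0.2 SD or more at the planned size.

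Two stronger readings are not supported:
- A reader might infer that pooling biases the arm difference. That needs the arm mix to differ between seasons. SAP 8.1 concedes that returning subjects are non-random cohorts, but nothing in the documents shows return differing by arm, and the effect cannot be sized. With balance within season there is no bias.
- A reader might infer that pooling amounts to discarding a sizeable share of the sample. Under the same balance the point estimate is no noisier; only its reported uncertainty is too wide.

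**What to change.** In SAP 8.6:
- Analyse log titers, and change in log titer, in a linear model with treatment and enrolling season as factors and subject-clustered robust variance.
- Define season as the season in which the sample was taken, not the cohort year enrolled.
- For seroconversion and seroprotection, use a season-stratified or season-adjusted analysis that keeps the subject clustering. An ordinary Mantel-Haenszel test would drop it.
- Report season-specific estimates beside the pooled one.

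The cost is a sentence or two of SAP text and one degree of freedom with two seasons or two with three. No new data are needed, since the collection season is already on every cryovial.

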### **12.1.1 Sample Collection Guidelines**

Subjects electing to participate in the optional correlative studies that become available after the Vanguard year will contribute two blood samples, one at baseline and a second sample two-four weeks after vaccination. At the first time point, 10 ml of blood will be collected in serum tubes for immune function analyses. At the second time point, 20 ml will be collected for immune function testing. At one of these timepoints, an additional 10 ml of blood will be collected in DNA collection tubes (only if the subject consents to banking of their blood for genetic testing).

Following the blood draw, the sampling tube should be stored at room temperature for a minimum of 60 minutes and a maximum of 2 hours to allow the blood to clot before centrifugation. The tube must be stored vertically and not shaken. Beyond 2 hours, the sampling tube must be refrigerated at a temperature of 2°C to 8°C and must be centrifuged within a maximum of 24 hours. After being allowed to clot for a minimum of 60 minutes to a maximum of 2 hours at room temperature (or after being refrigerated for 2 to 24 hours after collection), blood samples for serum antibody response assessment will be centrifuged before being divided into at least 3 aliquots, if possible. Sera will be placed in cryovials labeled with the study ID, collection number (#1 or #2), and collection season (i.e. 2016/17). Cryovials will be frozen at -20 degrees (or colder) and stored at the study sites. Once blood collection is completed or at the end of each influenza season, samples will be batch shipped to Brigham and Women's Hospital (U.S. sites) and Peter Munk Cardiac Centre (Canadian sites) for further analysis.

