6. DEFINITIONS

With most efficacy endpoints being time to event data, specification of censoring is critically important. Censoring rule will be specific to whether the endpoints are analyzed based on mITT analysis or ITT analysis.

An endpoint event is defined as all-cause death or cardiopulmonary hospitalization.

For mITT analysis: All randomized unique patients who received vaccinations at the beginning of enrolling seasons are included. If a patient does not return for re-vaccination for a subsequent season as per the randomization-once strategy, that patient is not included for that or any subsequent enrolling seasons. Each patient can contribute events in multiple consecutive seasons in which they are vaccinated. Events are included in the analysis if they occurred after 2 weeks post vaccination but before July 31 of the enrolling season. Any event occurring within 2 weeks after vaccination will not count as an event. If a patient dies within 2 weeks after vaccination, time to event will be censored on the date of death. If a patient experiences a non-fatal event within 2 weeks after vaccination, that event will not count as an event. If a patient has not experienced any endpoint event before July 31 of each enrolling season, time to event is censored at the last date known to be alive before July 31 of each enrolling season. If the last date known to be alive is on or after July 31 of the enrolling season, time to event is censored as of July 31. Time to event for each enrolling season is the elapsed time from vaccination and is determined as $\text{event/censoring date} - \text{vaccination date} + 1$.

For ITT analysis: All randomized unique patients are included, regardless of whether they were vaccinated on study or not, and followed through July 31, 2019, the date of data-cutoff. If a

patient has not experienced any endpoint event before July 31, 2019, time to event is censored at the last date known to be alive before July 31, 2019. If the last date known to be alive is on or after July 31, 2019, time to event is censored as of July 31, 2019. Time to event is an elapsed time from randomization and is determined as event/censoring date – randomization date + 1.

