8. STATISTICAL METHODS

8.1 General Principles

All statistical data analyses will be performed using SAS (SAS Institute, Inc., Cary NC) and R (R Foundation for Statistical Computing, Vienna, Austria. <http://www.R-project.org>).

Analyses of efficacy and safety endpoints will employ the mITT analysis as described in Section 5, except for the analysis of baseline data and the secondary efficacy endpoints in 4.2.1, total (first recurrent) cardiopulmonary hospitalizations or all-cause death across all enrolling seasons, and in 4.2.3, time to first occurrence of all-cause death or cardiopulmonary hospitalization, both across all enrolling reason, which will employ the ITT analysis.

With the mITT analysis to efficacy and safety analysis, each subject will potentially contribute endpoints more than once over multiple influenza seasons, and endpoints in each subject may be correlated. In order to account for the intra-subject correlation over multiple influenza seasons, a robust variance estimator will be used in statistical inference. Due to the randomization-once strategy, those returning for re-vaccination following the initial vaccination after randomization constitute non-random cohorts. This may introduce bias due to potential differential survivorship and drop-out after the initial randomization.

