In addition to the analysis of the clinical and immune outcomes, we will evaluate the association between antibody titers post-vaccination and subsequent hospitalizations using Poisson or negative binomial regression models to investigate the association of number of days in hospital per month on the log of the titers, controlling for treatment and other important covariates.

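### SAP 8.6 relates post-vaccination titer to clinical outcomes without a landmark, so a hospitalization up to 18 days before the blood draw can count as an outcome of a titer measured later

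*SAP*

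**What the plan says.** **Exposure.** Under Protocol 9.3.1 a sub-study subject "will be scheduled for a follow-up visit between two-four weeks (+ 4 days) post-vaccination". Protocol 12.1.1 describes two samples, "one at baseline and a second sample two-four weeks after vaccination". SAP 4.4 and 8.6 nevertheless label the second measurement as week 4. Protocol 9.3.1 adds: "Subjects unable to participate for a follow up blood draw will not be included in the immune response sub-study".

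**Outcome window.** SAP 6 states for the mITT analysis: "Events are included in the analysis if they occurred after 2 weeks post vaccination but before July 31 of the enrolling season". It also fixes the origin: "Time to event for each enrolling season is the elapsed time from vaccination". SAP 8.1 makes this the default: "Analyses of efficacy and safety endpoints will employ the mITT analysis as described in Section 5". The exceptions it lists are the baseline data and secondary endpoints 4.2.1 and 4.2.3.

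**Titer-outcome analyses.** SAP 8.6 contains three:
- Log-rank tests: "Clinical outcomes will be compared between those with and those without overall seroconversion and seroprotection". The sentence does not say which outcomes, or from what date.
- A Cox model that names the primary endpoint and has the post-vaccination geometric mean titer as a model term.
- A Poisson or negative binomial model for the "association between antibody titers post-vaccination and subsequent hospitalizations". This wording is prospective but gives no start date.

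SAP 8.6 mentions no landmark, delayed entry, time-dependent exposure or rule for events before the draw.

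**The concern.** SAP objective 2.3.2 is to test whether higher antibody concentrations go with a lower rate of death or cardiopulmonary hospitalization. An event that happened before the blood was drawn cannot bear on that. Entering the later titer as a fixed covariate from day 14 reverses the time order for those events.

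They will be in the database: the Protocol 9.4 schedule places a cardiopulmonary event assessment at the week 2-4 visit itself.

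The gap need not be neutral. Vaccination runs from August to January, so an influenza infection after vaccination could cause both a hospitalization and a rise in titer before the draw. That would place events among the seroconverters. In the other direction, Protocol 5.1 reports that reduced titers track the severity of heart disease, so sicker patients may have both low titers and early hospitalizations. At stake is how the correlate-of-protection analysis can be read.

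**Working it through.** **1. Length of the gap.** Events count after day 2 × 7 = 14. The draw falls between day 14 and day 4 × 7 + 4 = 32. The gap is therefore 0 to 32 − 14 = 18 days.

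**2. The plan's event rates.** The documents give no figure for the titer-outcome analyses, so I first checked that the rates used below reproduce the plan's projection (SAP 7: 9%, 8% and 7% by season, 30% of events being deaths, 30% not revaccinated).

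Retention to season 2 = (1 − 0.09 × 0.30) × 0.70 = 0.6811. To season 3 = 0.6811 × (1 − 0.08 × 0.30) × 0.70 = 0.4653.

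- 2016-17: 500 × 0.09 = 45.0
- 2017-18: 2,933 × 0.09 + 500 × 0.6811 × 0.08 = 291.2
- 2018-19: 2,933 × 0.09 + 2,933 × 0.6811 × 0.08 + 500 × 0.4653 × 0.07 = 440.1
- 2019-20: 2,933 × (0.09 + 0.6811 × 0.08 + 0.4653 × 0.07) = 519.3

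The total is 1,295.6, against 1,296 stated.

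**3. Events between day 14 and the draw.** From the documents: up to 3,000 sub-study subjects (Protocol 12.0), season rates of 7-9%, a 30/70 split of deaths and hospitalizations, and vaccination from August to January. My assumptions: constant hazard from day 14 to July 31, the full 3,000 subject-seasons, the 70% share applying in the gap, and the vaccination and draw dates shown.

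Let *r* be the season rate, *w* the days from day 14 to July 31, and *g* the gap in days.

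- Hazard *h* = −ln(1 − *r*)/*w*
- Expected events before the draw = 3,000 × mean of [1 − exp(−*h g*)]
- Hospitalizations among them = 0.70 × that number

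Central case: vaccination on 15 October, *w* = 289 − 14 = 275, *r* = 0.09, so *h* = 0.0943/275 = 0.000343 per day. Expected events in all: 3,000 × 0.09 = 270. With draws spread evenly over days 14-32 the mean gap is 9 days, giving about 9.2 events, of which 0.70 × 9.2 ≈ 6.5 are hospitalizations.

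| Vaccination | Rate | Draw timing | Events before draw | Hospitalizations (70%) | Share of all expected events |
|---|---|---|---|---|---|
| 15 Oct | 9% | even, days 14-32 | 9.2 | 6.5 | 2.4% of 270 |
| 15 Oct | 9% | all day 28 | 14.4 | 10.1 | 3.7% of 270 |
| 15 Oct | 9% | all day 32 | 18.5 | 12.9 | 4.8% of 270 |
| 15 Aug (low end) | 7% | even, days 14-32 | 5.8 | 4.1 | 1.9% of 210 |
| 31 Jan (high end) | 9% | all day 32 | 30.3 | 21.2 | 7.9% of 270 |

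Only the hospitalization column applies. The other 30% are deaths, and a subject who dies before the draw has no titer.

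**4. Effect on an estimate (illustration).** Suppose the true hazard ratio per doubling of titer is 0.80 and the pre-draw events carry no association. Then 0.80^(1 − 0.024) = 0.804 and 0.80^(1 − 0.079) = 0.814. If the pre-draw events are themselves linked to titer, the shift could be larger and in either direction.

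**5. Events left after the fix (central case).** Risk time from the actual draw: 270 − 9.2 ≈ 261. Fixed day-32 landmark: 270 − 18.5 ≈ 252.

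**The case against.** The strongest reply is that SAP 8.6 never states a time origin. The mITT default in SAP 8.1 covers efficacy and safety endpoints, and the SAP lists the correlative endpoints separately. The log-rank sentence does not name the primary endpoint, and the count model is already worded prospectively. On this view the plan is silent rather than wrong.

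That holds in part. For the log-rank tests, the day-14 start follows from the default and is not written in 8.6. For the Cox model the reply fails: it names the primary endpoint, SAP 6 sets that endpoint's window and clock, and 8.6 changes neither.

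Three stronger readings are tempting but not supported:

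- **Immortal-time bias between titer groups.** The draw is required of responders and non-responders alike. The death-free stretch before it is a shared survivor restriction and gives neither group an advantage.
- **A known bias against finding protection.** Infection before the draw would act that way, but low titers in sicker patients would act the other way. The documents size neither.
- **About 30 misattributed events, or 11%.** That count includes deaths, which cannot occur before the draw in included subjects. It also needs every subject vaccinated on 31 January and drawn on day 32, whereas Protocol 7.2 stresses early recruitment.

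It is also fair to say that the stakes are limited: this is a non-randomized association in an optional sub-study.

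**Conclusion.** The concern holds for the Cox model as written, and for the log-rank tests through the mITT default. A non-fatal hospitalization up to 18 days before the draw counts as an outcome of the later titer. The expected size is about 6 to 13 hospitalizations (2-5% of events) in the central case and about 4 to 21 (2-8%) over the range examined. These figures rest on constant hazard, the full 3,000 subject-seasons, the plan's 7-9% season rates and a 70% hospitalization share; a smaller sub-study scales the counts down but not the percentages. The direction of the bias is uncertain.

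A reader might infer that the trial's main result is at risk. It is not: the randomized primary comparison does not use the titer. The point concerns only the reading of objective 2.3.2, and it is worth settling in the SAP because the remedy is cheap.

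**What to change.** In SAP 8.6:

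1. Start risk time for all titer-outcome log-rank and Cox analyses at the date of the second blood draw, and count the first event after it through July 31.
2. Define *subsequent* in the Poisson or negative binomial analysis by the same start date.
3. Treat non-fatal events between vaccination and the draw as SAP 6 already treats those in the first 2 weeks: not counted, subject kept. Dropping subjects for a day-15 event while keeping those with a day-13 event would be inconsistent.
4. Report the pre-draw events separately by titer group, and exclude those subjects in a sensitivity analysis. This addresses a titer raised by the same infection that caused the admission.
5. Confirm that the draw date is captured. Protocol 12.1.1 labels vials with study ID, collection number and season only, and neither document lists the draw date as a recorded field. If it is not available, use a fixed day-32 landmark.

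The cost is SAP wording and a check of the database. Roughly 2-8% of sub-study events go unused, namely hospitalizations that precede the titer. The day-32 fallback loses somewhat more, as shown in the working.
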